13.1.3 Hospitalization-Free Survival On Treatment

Hospitalization-free survival days, and number of days on treatment out of hospitalization and skilled nursing facility be compared between roxadustat vs. placebo using ANCOVA with baseline Hb, baseline eGFR and other randomization stratification factors as baseline covariates.

13.1.4 Pooled Analyses

The analytical methods for the composite safety endpoints of interest will be described in a region-specific pooled SAP to reflect the nature of the pooling of these endpoints across multiple studies in the Phase 3 program and the region-specific safety endpoints.

13.2 CLINICAL LABORATORY PARAMETERS

Descriptive statistics for laboratory values (in US conventional and SI units) and changes from baseline at each assessment time point will be presented by treatment group for laboratory parameters collected in the study that include but are not limited to the following:

Hematology: Hemoglobin, hematocrit, RBC count, MCV, WBC count, WBC differential, and platelet counts;

Chemistry: Alkaline phosphatase, ALT, AST, total bilirubin, CPK, LDH, total protein, albumin, fasting glucose, phosphate, uric acid, BUN, creatinine, sodium, and potassium; eGFR, HbA1C; UACR

To assess potentially clinically significant (PCS) laboratory abnormalities (Appendix 2), the number and percentage of subjects with post-baseline lab values outside a pre-defined range (low or high) or limit of change will be tabulated by treatment group. Laboratory test values will be considered PCS if they meet the criteria listed in an appendix. The percentages are to be calculated relative to the number of subjects with available non-PCS baseline values and at least one post-baseline assessment. The numerator is the total number of subjects with at least one post-baseline PCS value. Shift tables may be presented. A supportive listing of subjects with post-baseline PCS values will be provided including the patient ID, study center, baseline, and post-baseline values. A listing of all AEs for subjects with PCS laboratory values will also be provided.

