7.1.2.1 Day 1 (Week 0)

All assessments are to be completed prior to study drug administration.

- Inclusion/Exclusion criteria verification
- Complete physical examination
- Weight
- Blood pressure, heart rate, respiratory rate, temperature
- Laboratory tests
 - Urinalysis, including microalbumin/creatinine ratio
 - CBC with WBC differential

- Serum chemistry
- Lipid panel (fasting, whenever possible)
- Serum iron, ferritin, TIBC, TSAT
- CHr
- HbA1c
- Reticulocyte count
- Special laboratory analytes: Hepcidin and high sensitivity-C-reactive protein (hs-CRP)
- Archival serum/plasma samples(optional donation, separate consent form)
- HemoCue assessment
- Point of care qualitative urine pregnancy test for women of child bearing potential only
- HRQoL questionnaires (SF-36, FACT-An, and European Quality Of Life Questionnaire in Five Dimensions, Five Levels [EQ-5D-5L])
- 12-lead electrocardiogram
- Adverse event recording
- Concomitant medication recording
- Procedures and nondrug therapy recording
- Dispense study drug (2 weeks supply)

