7.1.2.3 Weeks 4 to 24 (Every 2 weeks, ± 2 days)

- Laboratory tests (must be performed prior to next dosing cycle):
 - Weeks 4, 8, 12, and 20: CBC with WBC differential
 - Week 6 followed by every visit where no CBC is collected: Hb only
 - Weeks 4, 8, 12, and 20: Serum chemistry
 - Weeks 6 and 16: LFTs and CPK only
 - Weeks 4, 8, 12, and 20: Lipid panel (fasting whenever possible)
 - Weeks 4, 8, 12, and 20: Serum iron, ferritin, TIBC, TSAT
 - Weeks 4, 6, 8, 12, and 20: CHr
 - Week 12 only: HbA1c
 - Weeks 8, 12, and 20: Reticulocyte count
 - Weeks 4, 12, and 20: Special laboratory analytes (hepcidin, hsCRP)
 - Weeks 4, 12, and 20: Archival serum/plasma samples (optional donation, separate consent form)
- HemoCue assessment
- Weeks 12 and 24: Targeted physical examination
 - Weeks 12 and 24: Point of care qualitative urine pregnancy test for women of child bearing potential only
- Dose adjustment review beginning at Week 4 followed by every 4 weeks thereafter (except/or more frequently in the event of excessive hematopoiesis). Refer to Section 2.1 and Appendix 1.
- Week 12 only: HRQoL questionnaires (SF-36, FACT-An, and EQ-5D-5L)
- Adverse event recording
- Concomitant medication recording
- Procedures and nondrug therapy recording

- Dispense study drug
 - Weeks 4 to 22 (2 week supply)
 - Week 24 (4 week supply)

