7.1.2.4 Week 28 to End of Treatment (Every 4 weeks, ± 3 days)

- Laboratory tests (must be performed prior to next dosing cycle):
 - Week 28 followed by every 8 weeks: CBC with WBC differential
 - Week 28 followed by every visit where no CBC is collected: Hb only
 - Week 28 followed by every 8 weeks: Serum chemistry
 - Weeks 28, 36, 44, and 52 followed by every 12 weeks: Lipid panel (fasting whenever possible)
 - Week 28 followed by every 8 weeks: Serum iron, ferritin, TIBC, TSAT
 - Week 28 followed by every 8 weeks: CHr
 - Week 28 followed by every 16 weeks: HbA1c
 - Weeks 44, 68 and 84: Reticulocyte count
 - Weeks 44, 68 and 84: Special laboratory analytes (hepcidin, hsCRP)
 - Weeks 44, 68 and 84: Archival serum/plasma samples (optional donation, separate consent form)
- HemoCue assessment
- Week 36 followed by every 12 weeks: Targeted physical examination
 - Week 36 followed by every 12 weeks: Point of care qualitative urine pregnancy test for women of child bearing potential only
- Weeks 28, 52, and 76: 12-lead electrocardiogram
 - Dose adjustment review every 4 weeks (except/or more frequently in the event of excessive hematopoiesis). Refer to Section 2.1 and Appendix 1.
- All visit weeks: BP and B.
- All visit weeks: BP and heart rate
- Weeks 28, 52, and 76: HRQoL questionnaires (SF-36, FACT-An, and EQ-5D-5L)
- Adverse event recording
- Concomitant medication recording

- Procedures and nondrug therapy recording
- Dispense study drug (4 weeks supply), except at End of Treatment

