7.4.2 Central Laboratory

All study related tests of blood specimens will be performed by a central laboratory.

Unscheduled and repeat laboratory tests will also be performed by the central laboratory. However, if the turnaround time from the central laboratory is not sufficiently rapid for clinical management of the subject, local laboratory test results may be used to make the necessary clinical judgments.

A Central Laboratory Manual with instructions on specimen collection, processing, storing, and shipping to the central laboratory will be provided to all participating sites.

Laboratory parameters to be measured in this study are as described in Table 5.

Table 5. Laboratory Tests

CBC:	Chemistry Panel:		Additional Laboratory Analytes:				
Basophils	Albumin	Phosphorus	Vitamin B ₁₂				
Eosinophils	Bicarbonate	Potassium	Folate				
Erythrocyte count (RBC)	BUN	Sodium	HIV and viral Hepatitis Panel:				
Hb	Calcium	Total protein		Anti-HCV Ab tests			
Hct	Chloride	Uric acid	HBsAg				
Leukocyte count (WBC)	CPK	Liver Function Tests	HIV ELISA				
Lymphocytes	Creatinine	ALP	Urinalysis:				
Mean corpuscular volume	Glucose	ALT		Microalbumin/creatinine ratio			
Mean corpuscular Hb	Lipase	AST		Standard UA with reflex microscopic and culture			
Mean corpuscular Hb concentration	Lactate dehydrogenase	Bilirubin, total and direct	Special Laboratory Analytes:				
Monocytes	Magnesium	GGT		Hepcidin			
Neutrophils	Serum Iron Profile		High-sensitivity CRP				
Neutrophils, immature (banded)			Serum Lipid Panel:				
Platelets					Ferritin	TIBC	Total Cholesterol
Reticulocyte count					Iron	TSAT	HDL
	Reticulocyte Hb content				LDL		
			Triglycerides				

Abbreviations: ALP = alkaline phosphatase; ALT = alanine aminotransferase; AST = aspartate aminotransferase; BUN = blood urea nitrogen; CBC = complete blood count; CPK = creatine phosphokinase; CRP = C-reactive protein; ELISA = enzyme-linked immunosorbent assay; GGT = gamma-glutamyl transferase; Hb = hemoglobin; HbA1c = glycated hemoglobin; HBsAg = hepatitis B surface antigen; Hct = hematocrit; HCV = hepatitis C virus; HDL = high-density lipoprotein; HIV = human immunodeficiency virus; LDL = low-density lipoprotein; RBC = red blood cell; TIBC = total iron binding capacity; TSAT = transferrin saturation; WBC = white blood cell.

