5.4 ADDITIONAL DATA HANDLING RULES AND PRESENTATION SPECIFICATIONS

The following general guidelines will apply to all statistical analyses and data presentations:

- Baseline is defined as the last available value obtained prior to the first dose of study drug, unless otherwise specified in this SAP.
- Hb baseline is defined as the mean of the last four available values obtained prior to the first dose, including the Day 1 pre-dose value.
- eGFR and urine albumin-to-creatinine ratio (UACR) baseline will use the mean of all available central lab values prior to the first dose of study drug, including the Day 1 pre-dose value.
- Baselines for reticulocyte count, reticulocyte hemoglobin content (CHr), hepcidin, hs-CRP, serum iron parameters (transferrin, TIBC, TSAT, Ferritin, sTfR, and iron), blood pressures and heart rate are defined as the mean of values obtained within two weeks prior to the first dose.
- Randomization stratification factors derived from actual data (not the ones from the randomization system) will be used in all applicable analysis models. A table will show the discrepancies between the two.
- Analysis visits (instead of the nominal visits from CRF) derived from visit dates and visit time windows will be used in all analyses, tables, listings and figures. Unscheduled visits within an allowable window will be grouped into the closest scheduled visits based on the visit window specified in Appendix 1. For subjects who have more than one measurement at a scheduled visit, the last measurement will be used, with the exception of CPK, WBC, liver function tests (i.e., ALT, AST, GGT, ALP, and total bilirubin), in which the maximum measurement will be used.

- By default, US conventional units will be used for laboratory value presentations. A set of lab summary tables in SI units will also be provided based on TLF index.
- Age is calculated as of date that the informed consent form was signed.
- age = INTCK('YEAR', Birth Date, Date of Informed Consent, 'C')
where INTCK is a SAS function.
- Duration of treatment or days in treatment is calculated as: last dose date – first dose date +1
- Body weight, height and temperatures will converted using the following formula:
 - kg = lb/2.2
 - cm = 2.54 x in
 - C° = (5/9) x (F° – 32)
- eGFR will be calculated using the following Modification of Diet in Renal Disease (MDRD) equation:

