6. Time to rescue therapy (composite of blood/RBC transfusion, ESA use, and IV iron) in the first 52 weeks of treatment will be compared using Inverse Probability of Censoring Weighted (IPCW) model detailed in Appendix A or Cox Proportional Hazards model as deemed appropriate. The Cox regression model will adjust for baseline Hb, baseline eGFR and other randomization stratification factors. Hazard ratio and its associated 95% CI will be computed between the roxadustat group versus pooled placebo. Superiority will be declared if the upper bound of the 2-sided 95% CI of the hazard ratio does not exceed one. Proportion of subjects who received rescue therapy over the treatment period will be derived using Kaplan-Meier approach.
7. Mean CFB in the SF-36 Vitality subscore averaged over Weeks 12 to 28 for the two treatment groups will be compared using an MMRM model as outlined above. A subgroup of subjects with baseline vitality subscore below 50 will be analyzed as a sensitivity analysis.
8. Progression of CKD measured by rate of change in eGFR over time adjusted by baseline eGFR, censored at chronic dialysis or kidney transplant will be analyzed using random slope and intercept model. Annualized eGFR slope over time is estimated by a random slope and intercept model using all available eGFR values (one baseline and all post-treatment values up to End of Treatment Period or start of chronic dialysis or kidney transplant) adjusted by Baseline Hb, Region, CV history at Baseline and the interaction terms Baseline eGFR by time point and Baseline Hb by time point). All assessments collected after initiation of chronic dialysis or kidney transplant will be excluded from the analysis.
9. Time to blood/RBC transfusion in the first 52 weeks of treatment will be compared using Inverse Probability of Censoring Weighted (IPCW) model detailed in Appendix A or Cox Proportional Hazards model as deemed appropriate. The Cox regression model will adjust for baseline Hb, baseline eGFR and other randomization stratification factors. Hazard ratio and its associated 95% CI will be computed between the roxadustat group versus pooled placebo. Superiority will be declared if the upper bound of the 2-sided 95% CI of the hazard ratio does not exceed one. Proportion of subjects who received blood/RBC transfusion over the treatment period will be derived using Kaplan-Meier approach.

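### The eGFR-slope analysis could adjust for the Day 1 UACR that the trial already collects: an optional gain in precision, not a correction of bias

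*SAP*

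**What the plan says.** **Collection.** Protocol 7.1.2.1 (Day 1, before dosing) lists "Urinalysis, including microalbumin/creatinine ratio". Table 5 in Protocol 7.4.2 places "Microalbumin/creatinine ratio" under Urinalysis, not in the chemistry panel. The Schedule of Assessments (Protocol Appendix 2) marks urinalysis in the Day 1 column only. Serum chemistry, which supplies creatinine for eGFR, recurs on treatment: "Weeks 4, 8, 12, and 20: Serum chemistry" and then "Week 28 followed by every 8 weeks: Serum chemistry".

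**Use in the SAP.** Beyond the abbreviation list, UACR appears twice. SAP 5.4 gives a baseline rule: "eGFR and urine albumin-to-creatinine ratio (UACR) baseline will use the mean of all available central lab values". SAP 13.2 names it at the end of the chemistry list ("eGFR, HbA1C; UACR"), under the statement that "changes from baseline at each assessment time point will be presented by treatment group for laboratory parameters collected in the study".

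**The slope model.** SAP 12.3 item 8 estimates the annualised eGFR slope with a random slope and intercept model. Its adjustment terms are "Baseline Hb, Region, CV history at Baseline and the interaction terms Baseline eGFR by time point", followed by baseline Hb by time. SAP 5.3 and 12.3 place the item in the fixed sequence at the 0.05 level.

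**The concern.** SAP section 2 names renal function as a secondary objective, and eGFR slope is the renal endpoint in the tested sequence. The trial takes a second baseline renal measurement before dosing and then makes no analytic use of it. A pre-dose covariate can be added without risk to the randomised comparison. If it is related to the rate of eGFR decline, the slope difference is estimated more precisely.

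The stakes are modest but not confined to item 8. Testing moves on only after a rejection, so precision at item 8 also affects whether items 9 to 12 are reached.

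**Working it through.** **1. Count the planned UACR values** (Protocol 7.1.1 to 7.1.3, Table 5, Appendix 2).

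- Before dosing: 1 (Day 1). The screening lists contain none.
- Scheduled post-baseline visits through Week 52: Weeks 1 and 2 (2) + Weeks 4 to 24 every 2 weeks (11) + Weeks 28 to 52 every 4 weeks (7) = 20.
- UACR planned at 0 of these 20, at no later visit, and at neither EOT/ET nor EOS. The urine pregnancy tests at other visits do not yield a UACR.
- Serum chemistry planned at 8 of the 20: Weeks 4, 8, 12, 20, 28, 36, 44 and 52.

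The trial therefore has repeated eGFR for the slope, and one planned UACR that can serve only as a baseline covariate. The averaging rule in SAP 5.4 has one planned UACR value to average.

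**2. Compare the model with what is available.** The listed terms in item 8 are baseline Hb, region, CV history, baseline eGFR by time and baseline Hb by time. UACR terms: 0. The term that would matter for slope is UACR by time, since a main effect alone adjusts the eGFR level rather than its rate of change.

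**3. Size of the possible gain.** The plan states no figure to reproduce, and the documents give neither the relation of UACR to eGFR slope nor the variance components. Everything in this step is therefore an assumption.

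Let R² be the share of between-subject slope variance that log UACR explains beyond the terms already in the model. Let s be the between-subject share of the total variance of the estimated slope difference, the remainder being within-subject eGFR variability. Then:

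SE ratio = √(1 − s·R²), and equivalent gain in subjects = 1/(1 − s·R²) − 1.

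| Assumed R² | SE ratio, s = 1 | SE reduction | Subjects | SE ratio, s = 0.5 | SE reduction | Subjects |
|---|---|---|---|---|---|---|
| 0.05 | √0.95 = 0.975 | 2.5% | 5.3% | √0.975 = 0.987 | 1.3% | 2.6% |
| 0.10 | √0.90 = 0.949 | 5.1% | 11.1% | √0.95 = 0.975 | 2.5% | 5.3% |
| 0.20 | √0.80 = 0.894 | 10.6% | 25.0% | √0.90 = 0.949 | 5.1% | 11.1% |

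The columns with s = 1 are upper bounds, because they set within-subject variability to zero. The value s = 0.5 is illustrative.

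**The case against.** The strongest reply is that this is a preference. The model already carries baseline eGFR by time and baseline Hb by time, randomisation is stratified by eGFR, and leaving out one more prognostic variable neither biases the comparison nor contradicts the protocol. Nothing in the documents shows that UACR predicts eGFR slope, so the gain could be close to zero. All of that stands, and it is why the change is optional.

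A reader might also infer something stronger from SAP 13.2: that the trial will report a treatment effect on albuminuria that it does not measure. The documents do not support this.

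- Section 13.2 is descriptive and covers parameters collected in the study at their assessment time points. For UACR the only planned one is Day 1.
- SAP section 8 says that baseline summaries of other parameters appear in their change-from-baseline tables, which explains why UACR is on that list.
- UACR is not an endpoint in SAP 4.1 to 4.3 and has no limit in SAP Appendix 2. The renal endpoints rest on eGFR, creatinine and renal replacement therapy.

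A small residue remains. Protocol 7.3 allows unscheduled laboratory tests at the investigator's discretion, and SAP 5.4 and 17.2 assign unscheduled values to visit windows. A few unplanned UACR results could therefore appear in a by-visit table. That warrants a clarifying line and changes no conclusion.

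**Conclusion.** The point holds as an optional improvement. A baseline renal marker that is already scheduled has no role in the one renal analysis under alpha control, and adding it would need no new data. It should not be read as an error in the slope analysis or as a source of bias.

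The size of the benefit is unknown. Under an assumed R² of 5% to 20%, the standard error falls by at most 2.5% to 11%. If between-subject variance were half the total, it would fall by about 1.3% to 5%. Reading the upper bound as a firm saving of 5% to 25% in subjects would be wrong, because that requires no within-subject eGFR variability at all.

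**What to change.** Before database lock and unblinding, amend SAP 12.3 item 8 to:

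- add log(baseline UACR) and log(baseline UACR) × time to the random slope and intercept model;
- state one rule for missing Day 1 values, for example single imputation from baseline data, blind to treatment arm. A missing-value category does not suit a continuous covariate that also interacts with time;
- state how results reported only as below a limit enter the log. The rule in SAP 5.4 for such values is written for summary statistics.

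Protocol 9.5 requires the SAP to be final before the final database lock, so the timing fits.

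As an editorial note, add to SAP 13.2 that UACR is summarised at baseline only.

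The cost is two model terms and a few lines of SAP text, with no new visits or samples.

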9.4.4.1 Adverse Events

Adverse events will be coded using Medical Dictionary for Regulatory Activities (MedDRA).

An AE (classified by preferred term) occurring during the double-blind treatment period will be considered a treatment emergent adverse event (TEAE) if it was not present prior to the first dose of study medication, or it was present prior to the first dose of study medication but increased in severity during the double-blind treatment period. An AE that occurs more than 28 days after the last dose of study medication will not be counted as a TEAE.

The number and percentage of subjects reporting TEAEs in each treatment group will be tabulated by system organ class (SOC) and preferred term; by SOC, preferred term, and severity; and by SOC, preferred term, and relationship. If more than one event occurs with the same preferred term for the same subject, the subject will be counted only once for that preferred term

using the most severe and most related occurrence for the summarization by severity and by relationship to the study medication.

The overall distribution of TEAEs by severity and relationship to study medication will be summarized by treatment group.

The number and percentage of subjects reporting common ($\geq 5\%$ of subjects in any treatment group) TEAEs, Treatment-Emergent serious AEs (TESAE), fatal SAEs (ie, events that caused death), and AEs leading to discontinuation of study medication will be summarized by SOC, preferred term and treatment group, sorted in decreasing frequency overall

Treatment emergent adverse events will also be reported in terms of incidence rate per PEY.

Listings will be presented of subjects with SAEs, subjects with AEs leading to discontinuation, and subjects who died.

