In addition, cumulative incidence plots for subjects experiencing each of the TEAE categories above will be produced by treatment arm and combined group (pooled roxadustat and pooled placebo). Temporal profile of TEAEs of special interest may also be plotted by combined treatment group (pooled roxadustat vs. pooled placebo) showing the subjects in the y-axis and time to these TEAEs in the x-axis (Appendix 7).

Due to suspected differential dropout rates between roxadustat vs. placebo and the resulted biases on event rates, selected TEAEs and TESAEs will be summarized by PEY censoring for start of chronic dialysis or renal transplant, and also stratified by baseline eGFR category (<10, 10-<15, 15-<30, and ≥ 30 mL/min/1.73m²).

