13.3 VITAL SIGNS

Blood Pressures and Heart Rate baselines are defined as the mean of values obtained from the last 2 weeks of screening including Day 1 prior to the first dose.

Descriptive statistics for vital signs (e.g., systolic and diastolic blood pressure, MAP, pulse rate, and respiratory rate) and their changes from baseline at each visit and at the end of study will be presented by treatment group.

Vital sign values are potentially clinically significant (PCS) if they meet both the observed value criteria and the change from baseline criteria listed in *Table 13.3 - 1* below. The number and percentage of subjects with post-baseline PCS values will be tabulated by treatment group. The percentages are to be calculated relative to the number of subjects with baseline and at least one post-baseline assessment. The numerator is the total number of subjects with at least one post-baseline PCS vital sign value. Shift tables may be presented. A supportive listing of subjects with post-baseline PCS values will be provided including the patient ID, study center, baseline, and post-baseline values. A listing of all AEs for subjects with PCS vital signs will also be provided.

Table 13.3 – 1. Criteria for Potentially Clinically Significant Vital Signs

Vital Sign Parameter	Flag	Criteria*	
		Observed Value	Change from Baseline
Systolic Blood Pressure (mmHg)	High	≥ 170	Increase of ≥ 20
	Low	≤ 90	Decrease of ≥ 20
Diastolic Blood Pressure (mmHg)	High	≥ 110	Increase of ≥ 15
	Low	≤ 45	Decrease of ≥ 15
Pulse Rate (bpm)	High	≥ 120	Increase of ≥ 20
	Low	≤ 50	Decrease of ≥ 20
Weight (kg)	High	-	Increase of $\geq 10\%$
	Low	-	Decrease of $\geq 10\%$

*Except for body weight, a post-baseline value is considered as a PCS value if it meets both criteria for observed value and change from baseline.

Additional analyses may include but are not limited to subgroup analyses of blood pressure in patients without any change in BP meds during treatment period.

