13.4 ELECTROCARDIOGRAM (ECG)

Descriptive statistics for ECG parameters (e.g., Heart Rate, PR interval, QRS interval, QT interval, and QTc interval) at baseline and changes from baseline at each assessment time point will be presented by treatment group. QTc interval will be calculated using both Bazett ($QTcB = QT/(RR)^{1/2}$) and Fridericia ($QTcF = QT/(RR)^{1/3}$) corrections; and if RR is not available, it will be replaced with 60/HR in the correction formula.

ECG parameters values are potentially clinically significant (PCS) if they meet or exceed the upper limit values and changes (where applicable) listed in Table 13.4-1 below. The number and percentage of subjects with post-baseline PCS values will be tabulated by treatment group. The percentages are to be calculated relative to the number of subjects with available non-PCS baseline and at least one post-baseline assessment. The numerator is the total number of subjects with at least one post-baseline PCS ECG value. Shift tables may be presented. A listing for all subjects with post-baseline PCS value will be provided including the patient ID, study center, baseline, and post-baseline PCS values.

In addition, a listing of all TEAEs for subjects with PCS ECG values and a listing of subjects with post-baseline significant ECG abnormalities as reported by the investigators will also be provided.

Table 13.4 - 1. Criteria for Potentially Clinically Significant ECG

ECG Parameter	Unit	Higher Limit
QRS interval	msec	≥ 150
PR interval	msec	≥ 250
QTc interval	msec	> 500; Change from baseline > 60

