17.2 REPEATED OR UNSCHEDULED ASSESSMENTS OF SAFETY PARAMETERS

If a patient has repeated assessments prior to the start of double-blind study medication, then the results from the final assessment made prior to the start of study medication will be used as baseline, except where otherwise specified. If post-baseline assessments are repeated or unscheduled, the last post-baseline assessment within a visit window will be used as the study visit assessment for generating summary statistics. However, all post-baseline assessments will be used for PCS value determination and all assessments will be presented in the data listings.

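### Clinically significant laboratory, vital-sign and ECG abnormalities are tabulated only as crude ever/never percentages, so unequal exposure can create or hide a difference between arms

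*SAP*

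**What the plan says.** **PCS tables.** SAP 13.2 (laboratory) sets the numerator as follows: "The numerator is the total number of subjects with at least one post-baseline PCS value". The denominator is a head count: "The percentages are to be calculated relative to the number of subjects with available non-PCS baseline values and at least one post-baseline assessment". SAP 13.3 and 13.4 follow the same pattern: "The numerator is the total number of subjects with at least one post-baseline PCS vital sign value" and "The numerator is the total number of subjects with at least one post-baseline PCS ECG value". SAP 17.2 adds that "all post-baseline assessments will be used for PCS value determination".

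**Exposure.** Under SAP section 3, treatment may last less than 52 weeks for some subjects and may run to 3 years after the last randomization. Tests continue throughout. Protocol 7.1.2.4, for example, schedules "Week 28 followed by every 8 weeks: Serum chemistry".

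**What the SAP says about dropout.** SAP 13.1.2 notes that differential discontinuation might influence adverse-event percentages. It therefore adds exposure-adjusted rates, cumulative incidence and Cox models for a list of adverse-event categories. It then adds summaries per patient-exposure-year (PEY) for selected events, introduced with "Due to suspected differential dropout rates between roxadustat vs. placebo and the resulted biases on event rates". PCS values are not included in either remedy.

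**Protocol on adverse events.** Protocol 9.4.4.1 sets no restriction: "Treatment emergent adverse events will also be reported in terms of incidence rate per PEY".

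**The concern.** An ever/never count rises with the number of assessments. If one arm stays on treatment longer, its subjects have more visits at which a value can cross a limit, and a larger share is flagged even when the underlying rate is the same. The reverse can also happen: a genuinely lower rate in the longer-exposed arm can be offset by its longer observation.

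The SAP gives this reasoning for adverse events but does not carry it over to the PCS tables, which have the same structure. Those tables are normally read side by side by arm. A false signal could be raised from them, or a true one dismissed as an exposure artefact.

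**Working it through.** **1. No stated figure to reproduce.** The documents give no expected PCS rate, discontinuation rate or exposure by arm for these tables. The calculation below is therefore illustrative.

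**2. Inputs.** All are assumed, none comes from the documents:
- PCS rate *r*: 5 to 40 per 100 patient-years, the same in both arms
- dropout rate *d*: 0.2-0.3 per year on roxadustat, 0.3-0.6 on placebo
- administrative end *T*: 1, 2 or 3 years

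**3. Formulas**, with constant rates and s = r + d:
- crude proportion ever flagged = (r/s) × (1 − exp(−sT))
- observed time at risk per subject = (1 − exp(−sT))/s
- rate = crude proportion / time at risk

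**4. Worked case.** r = 0.10; d = 0.2 versus 0.4; T = 3.
- Roxadustat: s = 0.3; crude = (0.1/0.3) × (1 − exp(−0.9)) = 19.8%; time at risk 1.978 years; rate 10.0 per 100 patient-years.
- Placebo: s = 0.5; crude = (0.1/0.5) × (1 − exp(−1.5)) = 15.5%; time at risk 1.554 years; rate 10.0 per 100 patient-years.
- Crude ratio 19.78/15.54 = 1.27; rate ratio 1.00.

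| T (years) | Crude, roxadustat | Crude, placebo | Crude ratio | Rate ratio |
|---|---|---|---|---|
| 1 | 8.6% | 7.9% | 1.10 | 1.00 |
| 2 | 15.0% | 12.6% | 1.19 | 1.00 |
| 3 | 19.8% | 15.5% | 1.27 | 1.00 |

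**5. Range.** Over all the unequal-dropout combinations, the crude ratio runs from about 1.05 (for example r = 0.4, 0.2 versus 0.3, 1 year: 30.1% versus 28.8%) to 1.60 (r = 0.05, 0.2 versus 0.6, 3 years: 10.6% versus 6.6%). With equal dropout it is 1.00. Swapping the arms in the 3-year case gives 15.54/19.78 = 0.79.

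**6. Masking.** Keep 0.2 versus 0.4 and 3 years, and set the roxadustat rate to 0.08 against 0.10, a true ratio of 0.80. The crude figures are 16.2% versus 15.5%, a ratio of about 1.05.

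**7. Which time at risk.** SAP 13.1.2 runs event-free time to the last day of contact. After discontinuation, Protocol 7.1.2.6 continues follow-up for vital status, adjudicable events and key medication; beyond the ET and EOS visits no laboratory tests are scheduled. As a limiting case, suppose every event-free subject stays in contact to 3 years. Time counted per subject is then (r/s²) × (1 − (1 + sT)exp(−sT)) + (1 − crude) × T:
- Roxadustat: 0.253 + 0.802 × 3 = 2.659 years; rate 0.1978/2.659 = 7.4 per 100.
- Placebo: 0.177 + 0.845 × 3 = 2.711 years; rate 0.1554/2.711 = 5.7 per 100.
- Ratio 0.0744/0.0573 = 1.30, no better than the crude 1.27.

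The 13.1.2 denominator, used verbatim, would not remove the problem for laboratory values. SAP 13.5 already has a suitable rule for hemoglobin: censor at the last assessment.

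**8. What is already covered.**

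| PCS item | Existing time-based analysis |
|---|---|
| Liver enzymes, bilirubin | Time-to-first plot, without rate or hazard ratio (SAP 13.2.1) |
| High systolic or diastolic pressure | Worsened hypertension at the same limits, with hazard ratio and rate per PEY (SAP 4.2; 12.3 item 12) |
| Creatinine >1.5 × baseline | Time to doubling, a different limit (SAP 4.3) |
| Potassium, sodium, calcium, CPK, platelets, WBC | None |
| Low blood pressure, pulse, weight | None |
| QRS, PR, QTc | None |

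Excessive hematopoiesis, which is not an Appendix 2 criterion, also has a time-to-event analysis (SAP 13.5).

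**The case against.** A reader might infer that the SAP ignores exposure in its safety analyses. It does not. Besides the analyses listed above, labs, vital signs and ECG are summarized by visit, which does not accumulate chances over time. Clinically significant laboratory abnormalities are also reported as adverse events (Protocol 10.3.8), and those that are serious, Grade 3 or higher, or lead to discontinuation enter the SAP 13.1.2 analyses. The forest plot there mentions system organ classes, so rates at that level may be intended; the text is unclear. This narrows the gap without closing it.

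A reader might also infer that the tables will show a spurious excess on roxadustat. The documents do not support that: the SAP only suspects differential dropout and gives no size or direction. The absolute effect is small for rare criteria. At an assumed 0.02 per year with exponential time on drug averaging 1.6 versus 1.2 years, the crude figures are 0.02/(0.02 + 1/1.6) = 3.1% and 0.02/(0.02 + 1/1.2) = 2.3%, although the ratio is still about 1.3. ECGs are scheduled only at Weeks 28, 52 and 76 and at end of treatment or early termination, so a continuous-rate model describes them poorly.

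Nor does the PCS part contradict the protocol. Protocol 9.4.4.2 to 9.4.4.4 plan no exposure-adjusted PCS rates and no between-arm test. This is a weakness of presentation; the narrowing of the adverse-event rates is the only discrepancy between the documents. Finally, rate contrasts for every criterion and every preferred term would add many unadjusted comparisons and produce false signals of their own. That objection stands and limits the fix.

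**Conclusion.** The concern holds in a limited form. The three PCS tables are crude ever/never percentages over variable exposure, and the SAP's own reasoning about dropout applies to them, but its remedy does not reach them. If exposure differs by arm, the tables can create or mask a difference. The size cannot be derived from the documents: the range of 1.05 to 1.60 rests wholly on assumed dropout and event rates, constant hazards, and dropout unrelated to PCS risk. Under equal dropout the distortion vanishes.

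Separately, the commitment in Protocol 9.4.4.1 to report adverse-event incidence per PEY is narrowed in the SAP to listed categories and selected events.

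Both points bear on how safety is read. They do not touch the primary efficacy analyses. This is an inexpensive improvement, not a flaw that undermines the trial.

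**What to change.** 1. For PCS criteria without a time-based analysis, add by arm the number of subjects with a first PCS value per 100 patient-years at risk. Use the same subjects as the existing denominators. Censor event-free subjects at the last assessment of that parameter, as SAP 13.5 does for hemoglobin, and not at last day of contact.
2. Beside each rate, give the cumulative incidence of a first PCS value at the SAP 13.1.2 time points (6, 12, 18 and 24 months).
3. Restore adverse-event incidence per PEY by system organ class and preferred term, as the protocol states. Name the denominator: PEY in SAP 10.1 ends at the last dose, whereas the 13.1.2 time at risk runs to last contact.
4. Present all of this descriptively, without formal tests. Base between-arm safety statements on it and keep the crude percentages.
5. State that the rates assume a roughly constant hazard and uninformative dropout. SAP Appendix 8 already recognizes informative censoring for the time-to-event analyses.

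The cost is SAP wording and extra table columns from data already collected. The drawback is longer tables whose rates carry the assumptions in item 5.
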